**Time (time is in reference to Study Drug (ISIS 757456 or placebo) administration)**

a Pre-dose

## **APPENDIX B. LIST OF LABORATORY ANALYTES**

**Appendix B List of Laboratory Analytes**

Based on emerging data from this or future studies, additional tests not listed below may be performed on stored samples to better characterize the profile of ISIS 757456 or other similar oligonucleotides.

Clinical Chemistry Panel
 
 
• Sodium
 
• Potassium
 
• Chloride
 
• Bicarbonate
 
• Total protein
 
• Albumin
 
• Calcium
 
• Magnesium
 
• Phosphorus
 
• Glucose
 
• BUN
 
• Creatinine
 
• Creatinine Clearance
 
• Uric Acid
 
• Total bilirubin
 
• Direct (conjugated) bilirubin
 
• Indirect (unconjugated) bilirubin
 
• ALT
 
• AST
 
• Alkaline phosphatase
 
• Creatinine kinase
 
• GGT
 
 
Thyroid Panel
 
 
• TSH
 
• Free T4
 
• Free T3
 
	
Screening Tests
 
 
• Hepatitis B surface antigen
 
• Hepatitis C antibody
 
• HIV antibody
 
• FSH (women only, if applicable)
 
• Serum beta-subunit of human chorionic gonadotropin (βhCG) (women only, if applicable)
 
 
Coagulation
 
 
• aPTT (sec)
 
• PT (sec)
 
• INR
 
 
Efficacy
 
 
• Plasma AGT
 
 
Pharmacokinetics
 
 
• ISIS 757456 levels in plasma
 
 
Immunogenicity
 
 
• Anti-ISIS 757456 antibodies
 
 
Renal Urine Biomarkers
 
 
• NGAL
 
• NAG
 
• KIM-1
 
	
Hematology
 
 
• Red blood cells
 
• Hemoglobin
 
• Hematocrit
 
• MCV, MCH, MCHC
 
• Platelets
 
• White blood cells
 
• WBC Differential (% and absolute)
 
• Neutrophils
 
• Eosinophils
 
• Basophils
 
• Lymphocytes
 
• Monocytes
 
 
Exploratory
 
 
• Angiotensin II
 
• Renin (PRA)
 
• Renin (ARC)
 
• Plasma Aldosterone
 
• Angiotensin I
 
• Angiotensin (1-7)
 
• Angiotensin III
 
• Angiotensin IV
 
• B-type natriuretic peptide
 
• Atrial natriuretic peptide
 
• Plasma Nephilysin
 
• Endothelin I
 
	
Inflammatory
 
 
• Hs-CRP
 
 
Urinalysis
 
 
• Color
 
• Appearance
 
• Specific gravity
 
• pH
 
• P/C Ratio (UPCR)
 
• Protein
 
• Blood
 
• Ketones
 
• Urobilinogen
 
• Glucose
 
• Bilirubin
 
• Leukocyte esterase
 
• Nitrate
 
• Microscopic examination
 
• Angiotensinogen
 
• Albumin
 
• Creatinine
 
• Protein
 
• Sodium^3
 
• Cortisol
 
• Aldosterone
 
• A/C Ratio (UACR)
 

---	--	---	---

1 Plasma PK samples may also be used for profiling of drug binding proteins, bioanalytical method validation purposes, stability assessments, metabolite assessments, immunogenicity testing (or possibly for purposes of immunogenicity assay development and/or validation) or to assess other actions of ISIS 757456 with plasma constituents

2 Will be performed on abnormal findings unless otherwise specified

3 May be analyzed

## **APPENDIX C. PK SAMPLING SCHEDULE**

**Appendix C PK Sampling Schedule**

**PK Sampling Schedule**

D1	D3	D8	D15	D22	D29	D36	D43	D50	D57	D64	D78	D92	D120	D141
Pre-dose	Pre-dose	Pre-dose	Pre-dose	Pre-dose	Pre-dose	Pre-dose	Pre-dose	Pre-dose	Anytime	Anytime	Anytime	Anytime	Anytime	Anytime
1	1	1	1	1	1	1	1	1	1	1	1	1	1	1

SC = subcutaneous

D = Day

**APPENDIX D. GRADING SCALE FOR AES RELATING TO  
LABORATORY ABNORMALITIES**

**Appendix D Grading Scale for AEs Relating to Laboratory Abnormalities**

The following grading recommendations for AEs relating to lab test abnormalities and AEs at the injection site are based upon the CTCAE Version 5.0, November 2017.

Adverse Event	Mild	Moderate	Severe
Hematology			
aPTT prolonged	>ULN - 1.5 x ULN	>1.5 - 2.5 x ULN	>2.5 x ULN; bleeding
Eosinophils increased †	>ULN and >Baseline	-	Steroids Initiated
Fibrinogen decreased	<1.0 - 0.75 x LLN; if abnormal, <25% decrease from baseline	<0.75 - 0.5 x LLN; if abnormal, 25 - <50% decrease from baseline	<0.5 x LLN; if abnormal, ≥50% decrease from baseline
Hemoglobin decreased (Anemia)	Hemoglobin (Hgb) <LLN - 10.0 g/dL; <LLN - 6.2 mmol/L; <LLN - 100 g/L	Hgb <10.0 - 8.0 g/dL; <6.2 - 4.9 mmol/L; <100 - 80g/L	Hgb <8.0 g/dL; <4.9 mmol/L; <80 g/L; transfusion indicated
Hemoglobin increased**	Increase in >0 - 2 g/dL above ULN or above baseline if baseline is above ULN	Increase in >2 - 4 g/dL above ULN or above baseline if baseline is above ULN	Increase in >4 g/dL above ULN or above baseline if baseline is above ULN
INR increased	>1.2 - 1.5; >1 - 1.5 times above baseline if on anticoagulation	>1.5 - 2.5; >1.5 - 2.5 x baseline if on anticoagulation; monitoring only indicated	>2.5; >2.5 x baseline if on anticoagulation; dose adjustment indicated
Lymphocyte count decreased	<LLN - 800/mm  ; <LLN - 0.8 x 10  /L	<800 - 500/mm  ; <0.8 - 0.5 x 10  /L	<500 /mm  ; <0.5 x 10  /L
Lymphocyte count increased	-	>4000/mm  - 20,000/mm 	>20,000/mm 
Neutrophil count decreased	<LLN - 1500/mm  ; <LLN - 1.5 x 10  /L	<1500 - 1000/mm  ; <1.5 - 1.0 x 10  /L	<1000/mm  ; <1.0 x 10  /L
Platelet count decreased	<LLN - 75,000/mm  ; <LLN - 75.0 x 10  /L	<75,000 - 50,000/mm  ; <75.0 - 50.0 x 10  /L	<50,000/mm  ; <50.0 x 10  /L
White blood cell decreased	<LLN - 3000/mm  ; <LLN - 3.0 x 10  /L	<3000 - 2000/mm  ; <3.0 - 2.0 x 10  /L	<2000/mm  ; <2.0 x 10  /L
Chemistry			
Acidosis	pH <normal, but ≥7.3	-	pH <7.3
Alanine aminotransferase increased	>ULN - 3.0 x ULN if baseline normal 1.5 - 3.0 x baseline if baseline abnormal	>3.0 - 5.0 x ULN if baseline normal >3.0 - 5.0 x baseline if baseline abnormal	>5.0 x ULN if baseline normal >5.0 x baseline if baseline abnormal
Alkaline phosphatase increased	>ULN - 2.5 x ULN if baseline normal 2.0 - 2.5 x baseline if baseline abnormal	>2.5 - 5.0 x ULN if baseline normal >2.5 - 5.0 x baseline if baseline abnormal	>5.0 x ULN if baseline normal >5.0 x baseline if baseline was abnormal
Alkalosis	pH >normal, but ≤7.5	-	pH >7.5
Aspartate aminotransferase increased	>ULN - 3.0 x ULN if baseline normal 1.5 - 3.0 x baseline if baseline abnormal	>3.0 - 5.0 x ULN if baseline normal >3.0 - 5.0 x baseline if baseline abnormal	>5.0 x ULN if baseline normal >5.0 x baseline if baseline abnormal
Blood bilirubin increased	>ULN - 1.5 x ULN if baseline normal >1.0 - 1.5 x baseline if baseline abnormal	>1.5 - 3.0 x ULN if baseline normal >1.5 - 3.0 x baseline if baseline abnormal	>3.0 x ULN if baseline normal >3.0 x baseline if baseline abnormal
Cardiac troponin I increased	Levels above the upper limit of normal and below the level of myocardial infarction as defined by the manufacturer	-	Levels consistent with myocardial infarction as defined by the manufacturer

**Appendix D Grading Scale for AEs Relating to Laboratory Abnormalities (Continued)**

Adverse Event	Mild	Moderate	Severe
Cardiac troponin T increased	Levels above the upper limit of normal and below the level of myocardial infarction as defined by the manufacturer	-	Levels consistent with myocardial infarction as defined by the manufacturer
CD4 lymphocytes decreased	<LLN - 500/mm  ; <LLN - 0.5 x 10  /L	<500 - 200/mm  ; <0.5 - 0.2 x 10  /L	<200/mm  ; <0.2 x 10  /L
CPK increased*	>ULN - <6 ULN	6 - 10 x ULN	>10 x ULN
Creatinine increased**	>ULN - 1.5 x ULN if baseline normal > 1.0 - 1.5 x baseline if baseline abnormal	>1.5 - 3.0 x ULN if baseline normal >1.5 - 3.0 x baseline if baseline abnormal	>3.0 x ULN if baseline normal >3.0 x baseline if baseline abnormal
GGT increased	>ULN - 2.5 x ULN if baseline normal 2.0 - 2.5 x baseline if baseline abnormal	>2.5 - 5.0 x ULN if baseline normal >2.5 - 5.0 x baseline if baseline abnormal	>5.0 x ULN if baseline normal >5.0 x baseline if baseline abnormal
Hypercalcemia	Corrected serum calcium of >ULN - 11.5 mg/dL; >ULN - 2.9 mmol/L; Ionized calcium >ULN - 1.5 mmol/L	Corrected serum calcium of >11.5 - 12.5 mg/dL; >2.9 - 3.1 mmol/L; Ionized calcium >1.5 - 1.6 mmol/L; symptomatic	Corrected serum calcium of >12.5 mg/dL; >3.1 mmol/L; Ionized calcium >1.6 mmol/L; hospitalization indicated
Hyperglycemia††	Fasting glucose value ≥126 mg/dL (7.0 mmol/L)	Change in daily management to maintain fasting blood glucose <126 mg/dL (7.0 mmol/L); e.g. addition of oral antidiabetic agent; workup for diabetes	Insulin therapy initiated; hospitalization indicated
Hyperkalemia	>ULN - 5.5 mmol/L	>5.5 - 6.0 mmol/L; intervention initiated	>6.0; hospitalization indicated
Hypermagnesemia	>ULN - 3.0 mg/dL; >ULN - 1.23 mmol/L	-	>3.0 mg/dL; >1.23 mmol/L
Hypematremia	>ULN - 150 mmol/L	>150 - 155 mmol/L; intervention initiated	>155 mmol/L; hospitalization indicated
Hyperphosphatemia	Laboratory finding only and intervention not indicated	Noninvasive intervention indicated	Severe or medically significant but not immediately life-threatening; hospitalization or prolongation of existing hospitalization indicated
Hyperuricemia	>ULN without physiologic consequences	-	>ULN with physiologic consequences
Hypoalbuminemia	<LLN - 3 g/dL; <LLN - 30 g/L	<3 - 2 g/dL; <30 - 20 g/L	<2 g/dL; <20 g/L
Hypocalcemia	Corrected serum calcium of <LLN - 8.0 mg/dL; <LLN - 2.0 mmol/L; Ionized calcium <LLN - 1.0 mmol/L	Corrected serum calcium of <8.0 - 7.0 mg/dL; <2.0 - 1.75 mmol/L; Ionized calcium <1.0 - 0.9 mmol/L; symptomatic	Corrected serum calcium of <7.0 mg/dL; <1.75 mmol/L; Ionized calcium <0.9 mmol/L; hospitalization indicated
Hypoglycemia‡	≥54 mg/dL - <70 mg/dL ≥3.0 mmol/L - <3.9 mmol/L	<54 mg/dL (3.0 mmol/L) AND no assistance required to actively administer carbohydrates, glucagon, or take other corrective actions	Requires assistance of another person to actively administer carbohydrates, glucagon, or take other corrective actions
Hypokalemia	<LLN - 3.0 mmol/L	symptomatic with <LLN - 3.0 mmol/L; intervention indicated	<3.0 mmol/L; hospitalization indicated
Hypomagnesemia	<LLN - 1.2 mg/dL; <LLN - 0.5 mmol/L	<1.2 - 0.9 mg/dL; <0.5 - 0.4 mmol/L	<0.9 mg/dL; <0.4 mmol/L
Hyponatremia	<LLN - 130 mmol/L	125-129 mmol/L and asymptomatic	125-129 mmol/L symptomatic; 120-124 mmol/L regardless of symptoms
Hypophosphatemia	Laboratory finding only and intervention not indicated	Oral replacement therapy indicated	Severe or medically significant but not immediately life-threatening; hospitalization or prolongation of existing hospitalization indicated
Lipase increased	>ULN - 1.5 x ULN	>1.5 - 2.0 x ULN; >2.0 - 5.0 x ULN and asymptomatic	>2.0 x ULN with signs or symptoms
Serum amylase increased	>ULN - 1.5 x ULN	>1.5 - 2.0 x ULN; >2.0 - 5.0 x ULN and asymptomatic	>2.0 x ULN with signs or symptoms

**Appendix D Grading Scale for AEs Relating to Laboratory Abnormalities (Continued)**

Adverse Event	Mild	Moderate	Severe
Urine			
Proteinuria			
Adults	1+ proteinuria; urinary protein $\geq$ ULN - <1.0 g/24 hrs	2+ and 3+ proteinuria; urinary protein 1.0 - 3.4 g/24 hrs;	4+ proteinuria; Urinary protein $\geq$ 3.5 g/24 hrs;
Children	-	Urine P/C (Protein/Creatinine) ratio 0.5 - 1.9	Urine P/C >1.9
Hematuria	Asymptomatic; clinical or diagnostic observations only; intervention not indicated	Symptomatic; urinary catheter or bladder irrigation indicated	Gross hematuria; transfusion, IV medications or hospitalization indicated; elective invasive intervention indicated
Adverse Events at the Injection Site			
Adverse events at the injection site**	An event at the injection site (e.g. erythema, tenderness, itching) that is easily tolerated by the subject and does not affect the subject's usual daily activities	- Persistent (>24 hours) pain, phlebitis or edema; OR - Lipodystrophy, hair growth or alopecia, OR - Prolonged (>1 month) hypo/hyperpigmentation	- Ulceration or necrosis; severe tissue damage; operative intervention indicated, OR - Any event at the injection site that is incapacitating

†Grading for this parameter is derived from the Toxicity Grading Scale for Healthy Adult and Adolescent Volunteers Enrolled in Preventive Vaccine Clinical Trials, Sept 2007

\*Grading for this parameter is derived from the Division of AIDS (DAIDS) Table for Grading the Severity of Adult and Pediatric Adverse Events Version 2.0, Nov 2014

††Modified for consistency with ADA "Standards of Medical Care in Diabetes - 2018" Diabetes Care 2018;41(Suppl. 1):S13–S27. <https://doi.org/10.2337/dc18-S002>

‡Modified for consistency with ADA "Glycemic Targets: Standards of Medical Care in Diabetes - 2018", Diabetes Care 2018;41(Suppl. 1):S55–S64. <https://doi.org/10.2337/dc18-S006>

\*\*Adapted from the original CTCAE V5.0 scale

## **APPENDIX E. STRATIFICATION CRITERIA**

The **total** dose of the ACE or ARB taken per day is to be calculated based off the subject's stable regimen of antihypertensives at Screening. The stratification criteria are as follows:

ACE/ARB	Low Dose Stratum (total mg per day)	High Dose Stratum (total mg per day)
ACE		
benazepril	≤ 20	> 20
captopril	≤ 75	> 75
enalapril	≤ 10	> 10
fosinopril	≤ 20	> 20
lisinopril	≤ 20	> 20
perindopril	< 8	≥ 8
quinapril	< 40	≥ 40
ramipril	≤ 10	> 10
trandolapril	≤ 4	> 4
ARB		
azilsartan	≤ 40	> 40
candesartan	< 16	≥ 16
eprosartan	≤ 400	> 400
irbesartan	≤ 150	> 150
losartan	≤ 50	> 50
olmesartan	≤ 20	> 20
telmisartan	≤ 40	> 40
valsartan	≤ 160	> 160

Should a subject be on a stable regimen of an ACE/ARB at Screening that is not listed in the above table the Sponsor Medical Monitor or designee must be consulted prior to stratification.

**Official Title:** A Double-Blind, Placebo-controlled, Phase 2 Study to Assess the Safety, Tolerability and Efficacy of IONIS-AGT-LRX, an Antisense Inhibitor Administered Subcutaneously for 8 Weeks to Hypertensive Uncontrolled Blood Pressure

**NCT Number:** NCT04083222

**Document Date:** SAP Version 1.0: 04 December 2019

---

## 1 INTRODUCTION

This document provides a description of the study organization, study procedures, and the plan for the statistical analysis of the study data. Section 1 discusses study design, objectives, and endpoints; Section 2 provides the study procedures; Section 3 provides the detailed plan for the statistical analyses.

The purpose of this plan is to provide specific guidelines from which the analysis will proceed. Any deviations from these guidelines will be documented in the clinical study report (CSR).

Within this document, the terms 'patient' and 'subject' are both used to describe the individual who enrolls in this study.

### 1.1 Study Overview

This will be a Phase 2, double-blind, randomized, placebo-controlled study of ISIS 757456 conducted in uncontrolled hypertensive subjects on 2 to 3 antihypertensive medications. Subjects will be stratified based on a screening ACE/ARB dose (low vs high) and randomized in a 2:1 ratio to receive a once-weekly subcutaneous (SC) treatment and an additional loading dose on Study Day 3 with either ISIS 757456 80 mg or placebo for 8 weeks.

[figure not shown]
All subjects will complete a 13-week Post-Treatment Period.

[REDACTED] All Study Drug injections will be SC administered in the clinic.

This study will be conducted at multiple centers in the United States. Approximately 30 subjects are planned to be enrolled in this study.

The study will consist of Screening, Treatment, and Post-treatment. The overall length of a subject's participation will be approximately 25 weeks (up to 4 weeks for Screening, an 8-week Treatment Period, and a 13 weeks Post-Treatment Evaluation Period).

The study design and treatment schema are depicted as follows:

## 1.2 Objective

### 1.2.1 Primary Objective(s)

[figure not shown]
- To evaluate the effect of ISIS 757456 subcutaneous (SC) injection on plasma angiotensinogen (AGT) in uncontrolled hypertensive subjects on 2 to 3 antihypertensive medications

### 1.2.2 Secondary Objective(s)

- To evaluate the effect of ISIS 757456 on systolic blood pressure (SBP) in uncontrolled hypertensive subjects on 2 to 3 antihypertensive medications

### 1.2.3 Safety Objectives

- To evaluate the safety and tolerability of ISIS 757456 vs. placebo

### **1.3 Endpoints**

#### **1.3.1 Primary Endpoint**

[figure not shown]
- Percent change in plasma angiotensinogen from baseline to Study Day 57 (Week 9) compared to placebo

#### **1.3.2 Secondary Endpoints**

- Change on SBP from baseline to each scheduled, post-Baseline visit
- Change and percent change in plasma AGT from baseline to each scheduled, post-baseline visit

#### **1.3.3 Safety Endpoints**

- Incidence and severity of treatment-emergent adverse events (TEAE) (including hypotension and orthostatic hypotension), use of concomitant medications, abnormal findings in laboratory assessments, electrocardiogram (ECG), and vital signs

## 2 PROCEDURE

### 2.1 General Overview of Procedures

Ionis Pharmaceuticals, Inc. (or designee) will review all study data including source documents, case report forms, and laboratory reports. The study site will enter subject source data into the case report form. Some laboratory data will be transferred electronically from Endocrine Lab, Ludwig-Maximilians-University (LMU) Munich via Medpace Reference Laboratories (MRL), and from Pharmaceutical Product Development (PPD) Inc. (plasma concentration data) to Ionis Pharmaceuticals, Inc.

### 2.2 Randomization & Treatment Allocation

Subjects will be randomized after all screening assessments have been completed and after the Investigator has verified that they are eligible per criteria in protocol Sections 5.1 and 5.2. No subject may begin treatment prior to randomization and assignment of a unique subject identification number.

Eligible subjects will be stratified based on a screening ACE/ARB dose (low or high) and then subjects will be randomized 2:1 to receive ISIS 757456 or placebo as outlined in protocol Section 3.1. Eligible subjects must have a plasma AGT concentration  $\geq 20$   $\mu\text{g}/\text{mL}$  and have been on a stable regimen of 2 to 3 antihypertensive medications for at least 1 month prior to screening in order to participate in the study (see protocol Section 5.1 Inclusion Criteria). The Sponsor or designee will prepare the randomization list and utilize an automated IRT (Interactive Response Technology) system.

### 2.3 Conduct

The study will be conducted in accordance with current Good Clinical Practice (GCP) and International Conference on Harmonization (ICH) guidelines, the World Medical Association Declaration of Helsinki guidelines, the Food and Drug Administration (FDA) Code of Federal Regulations, and all other local regulatory requirements.

### 2.4 Data Monitoring

#### 2.4.1 Safety Data Monitoring

Ionis Pharmaceuticals, Inc. (or designee) is responsible for processing all reported adverse events (AEs). All serious adverse events (SAEs), reported to Ionis Pharmaceuticals, Inc. (or designee), are reviewed according to standard operating procedures. The medical monitor will review all AEs and SAEs on an ongoing basis throughout the study. Ionis Pharmaceuticals, Inc. (or designee) will prepare and submit safety reports to the health authorities worldwide in accordance with local requirements. If it becomes necessary to communicate new safety information, Ionis

Pharmaceuticals, Inc. (or designee) will also prepare a safety notification letter and transmit it to study site.

## **2.5 Data Management**

An electronic case report form (eCRF) utilizing an Electronic Data Capture (EDC) application will be used for this Study.

### **2.5.1 Case Report Form (CRF) Data**

BioClinica (or designee) is responsible for creating the EDC data entry screens, database and edit checks using definitions developed by Ionis Pharmaceuticals, Inc. Ionis Pharmaceuticals, Inc. is responsible for the review, data management querying and locking of the database.

Data are single-entered into the EDC system by the investigator site staff. Programmed edit checks (computer logic that checks the validity of the data entered and also prompts for missing data that is expected to be entered) are run and automatic queries are generated. Ionis Pharmaceuticals, Inc. reviews all data for accuracy and validity and generates additional queries in the EDC system when necessary. The data are corrected or an explanation concerning the query is provided in the EDC system. After all data are entered, source data verified, reviewed (by Data Management and Clinical Development) and queried, and all queries resolved, the database is locked.

### **2.5.2 Laboratory Data**

Ionis Pharmaceuticals, Inc. is responsible for the format of the laboratory electronic data transfers and the transfer schedule. Ionis Pharmaceuticals, Inc. is responsible for the review of the clinical laboratory data. This data is not stored in the EDC system. Investigator sites have access to the data via lab reports sent directly from the laboratory and online using the MRL ClinTrak® database.

### **2.5.3 Pharmacokinetics (PK) Data**

Ionis Pharmaceuticals, Inc. is responsible for the management and review of the plasma drug concentration data. Final data, which has been approved by Quality Assurance, will be stored in version-controlled repository.

## 3 ANALYSIS PLAN

### 3.1 Statistical Design Summary

Approximated 30 subjects will be randomized into two treatment cohort (ISIS 757456 80 mg or placebo). Eligible subjects will be stratified based on a screening ACE/ARB dose (low or high) and then subjects will be randomized 2:1 to receive ISIS 757456 or placebo.

The outcomes are descriptive. An interim analysis may be conducted after at least 50% of the subjects have been enrolled.

### 3.2 General Overview of Analyses

#### 3.2.1 Statistical Methods

Descriptive summary statistics including number of subjects, mean, median, standard deviation, standard error of mean, 25th percentile, 75th percentile, minimum, and maximum for continuous variables, and counts and percentages for categorical variables will be provided to summarize most data. Additional subject listings included case report form (CRF) data and derived outcomes from the data may be presented.

All statistical tests will be conducted using 2-sided tests with 5% Type I error rate unless otherwise stated. P-values will also be provided as an indicator to summarize how incompatibility between ISIS757456 and placebo cohort based on the statistical model. Unless specified, the stratification factor (screening ACE/ARB dose status) and treatment received are included in the model as independent variables.

PK parameters will be summarized using include number of subjects, mean, standard deviation, coefficient of variation (CV), geometric mean, median, minimum, and maximum.

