### 9.5.3. Dosing Errors

Study Drug (ISIS 757456 or placebo) errors (including overdose, underdose, and administration error) should be documented as Protocol Deviations. A brief description should be provided in the deviation, including whether the subject was symptomatic (list symptoms) or asymptomatic, and the event accidental or intentional.

Dosing details should be captured on the Dosing Case Report Form. If the subject takes a dose of Study Drug (ISIS 757456 or placebo) that exceeds protocol specifications and the subject is symptomatic, then the symptom(s) should be documented as an AE and be reported per Section 9.4.

An overdose is the accidental or intentional use of a drug in an amount higher than the dose being studied. An overdose or incorrect administration of study treatment is not itself an AE, but it may result in an AE. All AEs associated with an overdose or incorrect administration of Study Drug should be recorded on the AE eCRF. If the associated AE fulfills seriousness criteria, the event should be reported to the Sponsor immediately (i.e., no more than 24 hours after learning of the event).

**Should an overdose occur**, the Investigator or designee should refer to the Guidance to Investigator's section of the Investigator's Brochure and contact the Sponsor or designee within 24 hours.

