### **10.6.3. Efficacy Analysis**

The primary analysis will be the comparison of percent change from Baseline to Study Day 57 (Study Week 9) in plasma AGT between ISIS 757456 80 mg group and placebo group in the Per Protocol Set. The data will be analyzed using analysis of variance (ANOVA) with treatment and randomization stratification factor (low ACE/ARB dose regimen vs. high ACE/ARB dose regimen) as independent variables. In the case data departs substantially from normality, the nonparametric van Elteren test will be employed instead.

The secondary efficacy analyses will be performed in a similar way to the primary analysis, which include:

- Comparison of change and percent change from Baseline to each schedule post-Baseline visit in AGT between ISIS 757456 80 mg group and placebo group in Per Protocol Set (PPS) and FAS
- Comparison of change from Baseline to each schedule post-Baseline visit in in-clinic SBP and DBP between ISIS 757456 80 mg group and placebo group in PPS and FAS

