#### 3.2.2 Subject Population Analyzed

The following analysis populations are defined for this study:

- Full Analysis Set (FAS): All randomized subjects who have received at least 1 injection of Study Drug (ISIS 757456 or Placebo) and who have at least 1 post-Baseline efficacy or exploratory measurements.
- Per Protocol Set (PPS): All FAS subjects who received at least 7 of the 9 doses of Study Drug, did not alter antihypertensive medications during the Treatment Period and prior to Study Day 57, and have no significant protocol deviations that would be expected to affect efficacy or exploratory assessments.
- Safety Set: All subjects who are randomized and receive at least 1 dose of Study Drug.
- Pharmacokinetics (PK) Set: All subjects who are randomized and receive at least 1 dose of ISIS 757456 and have at least 1 evaluable PK sample.

In addition to the above analysis sets, it is recognized that some data displays will be provided for "All Screened", "Screening Failures" and "All Randomized" subjects but no data analysis will be executed in these populations.

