## **3.3 Primary Analysis**

### **3.3.1 Primary Efficacy Analysis**

The primary analysis will be the comparison of percent change from Baseline to Study Day 57 (Study Week 9) in plasma AGT between ISIS 757456 80 mg group and placebo group in PPS. The data will be analyzed using analysis of variance (ANOVA) with treatment and randomization stratification factor (screening ACE/ARB dose status) as independent variables. The normality assumption for the ANOVA model will be assessed by the Shapiro-Wilks test on the residuals. In the case data departs substantially from normality, the nonparametric Van Elteren test (van Elteren, 1960) will be employed instead. Additional analysis summary based on the FAS will also be provided.

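### The SAP's default model term is treatment received and is not clearly overridden, so a subject given the other arm's product could be grouped in the FAS by product given instead of as randomised

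*Combined protocol and SAP*

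**What the plan says.** The general statistical methods in SAP 3.2.1 set a default for the models. Unless specified, "the stratification factor (screening ACE/ARB dose status) and treatment received are included in the model as independent variables".

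The primary model is described again in SAP 3.3.1: "The data will be analyzed using analysis of variance (ANOVA) with treatment and randomization stratification factor (screening ACE/ARB dose status) as independent variables". Protocol 10.6.3 has the same form: "The data will be analyzed using analysis of variance (ANOVA) with treatment and randomization stratification factor". Neither says whether treatment means the arm assigned or the product given. SAP 3.4 says that the secondary comparisons follow the primary approach and names the two groups.

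The primary comparison is "between ISIS 757456 80 mg group and placebo group in PPS". For the same endpoint, "Additional analysis summary based on the FAS will also be provided". The secondary AGT and SBP comparisons are made in both the PPS and the FAS.

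FAS membership in SAP 3.2.2 begins with "All randomized subjects who have received at least 1 injection of Study Drug (ISIS 757456 or Placebo" and adds a requirement for one post-baseline measurement. It gives no rule for assigning the analysis group. Protocol 9.5.3 says that Study Drug "errors (including overdose, underdose, and administration error) should be documented as Protocol Deviations", also without a rule for the analysis group.

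**The concern.** A Full Analysis Set is normally compared as randomised, so that a handling error after randomisation cannot move a subject from one arm to the other. The default term in SAP 3.2.1 points the other way, and nothing visible in the SAP or protocol puts it right.

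This matters more here because the primary comparison is already in the PPS, which selects on events after randomisation: doses received, changes in antihypertensives, and deviations. The FAS is the efficacy set closest to the randomised comparison. If its group labels can also change after randomisation, no efficacy analysis is assured of keeping the arms as assigned.

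There is also a gap in definition. A subject given vials from both arms has no stated treatment received. The group would have to be chosen after the error was known, and possibly after unblinding.

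**Working it through.** **Reading the text**

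1. The default in SAP 3.2.1 has two terms: the stratification factor and treatment received. It yields where another section specifies something else.
2. SAP 3.3.1 names the same two terms. It ties the stratification factor to randomisation but leaves treatment unqualified. That can be read as a new specification or as a restatement of the default.
3. SAP 3.4 and protocol 10.6.3 do not settle the matter. The only place that says which treatment is meant is SAP 3.2.1, and it says received.
4. Overdose, underdose and missed doses do not change which product was received. Only wrong-arm product can change the label.
5. The seven-of-nine dose rule for the PPS does not by itself remove a wrong-arm subject. Study Drug is defined as ISIS 757456 or placebo, so a wrong-arm vial still counts as a dose. Exclusion rests on the judgement that the deviation is significant and likely to affect efficacy.

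**Size**

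The plan gives no figure on this point to reproduce. What follows is an illustration.

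*Inputs.* About 30 subjects (protocol 3.3) randomised 2:1 (SAP 3.1), taken as 20:10. Assumptions: the affected subject gets the other product for the whole course, responds as typical for that product, and the true effect is the same for everyone.

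*Formula.* Let a be the number of active-arm subjects given placebo and p the number of placebo-arm subjects given active.

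As-randomised contrast ÷ true effect = (20 − a)/20 − p/10

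SE factor = √(1/n₁ + 1/n₂), which is √(1/20 + 1/10) = 0.387 as randomised.

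| Error | As-randomised contrast ÷ true effect | As-received split | As-received SE factor |
|---|---|---|---|
| None | 1.00 | 20:10 | 0.387 |
| One active subject given placebo | 19/20 = 0.95 | 19:11 | 0.379 |
| One placebo subject given active | 1 − 1/10 = 0.90 | 21:9 | 0.398 |
| One swapped pair | 19/20 − 1/10 = 0.85 | 20:10 | 0.387 |

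*In AGT units.* Assume mean changes of −50% on drug and 0% on placebo; the visible documents give neither. With one placebo subject given active, the placebo mean as randomised is (1 × −50 + 9 × 0)/10 = −5%, so the difference is −50 − (−5) = −45 points. As received, it is −50 − 0 = −50 points.

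*Partial errors.* One wrong vial among nine leaves 8/9 = 89% of doses as assigned. The SAP does not say which treatment that subject received.

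**The case against.** The strongest reply is that the default applies only where nothing else is specified, and that SAP 3.3.1 and protocol 10.6.3 do specify the model. On that reading, treatment there means the arm assigned. This is a fair reading, but the text does not establish it: those sections repeat the default's two terms without saying as randomised. What stands is that this is an unresolved ambiguity and not a settled as-treated rule.

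The trigger is also narrow. Protocol 9.5.3 does not name wrong-arm product, though an administration error could include it. The roughly 30 × 9 = 270 administrations count opportunities, and the documents give no error rate. The PPS would probably exclude a subject given the wrong product, so the primary analysis is largely protected. SAP 3.1 calls the outcomes descriptive, although SAP 3.2.1 still sets two-sided 5% tests and p-values. All of this limits the likelihood and reach of the problem. None of it supplies the missing rule.

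Two stronger readings are tempting and are not supported:

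- **That the FAS loses its randomised basis.** Its membership still starts from randomised subjects. Only a group label could change, and only for a subject given the other arm's product.
- **That as-received grouping generally favours the drug.** In the illustration it returns the assumed true −50, while the as-randomised contrast is diluted to −45. That shows dilution, not inflation, and nothing in the documents fixes a direction in general. Nor would such errors be hidden: they are recorded as deviations, and SAP 3.2.4 lists deviations.

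**Conclusion.** The point holds as a wording defect. The SAP's default reads as treatment received, no later section clearly overrides it, and a subject given both products has no defined group. The consequence is limited to wrong-arm dosing errors. It falls mainly on the FAS summary of the primary endpoint and the FAS side of the secondary AGT and SBP comparisons.

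One full-course error would separate the as-randomised contrast from the true effect by 5% (active subject given placebo) or 10% (placebo subject given active). This rests on an exact 20:10 split, a uniform effect, and a typical response in the affected subject. If no such error occurs, the two analyses coincide.

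The case for as-randomised grouping is that it keeps the comparison set by randomisation and leaves no choice of arm after the event. It does not depend on showing that the as-received estimate would be biased towards the drug.

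**What to change.** - **FAS efficacy models.** In SAP 3.2.1, replace treatment received with randomised treatment, and use the same term in SAP 3.3.1 and 3.4.
- **PPS.** State in SAP 3.2.2 that receipt of wrong-arm product is a significant deviation that excludes the subject. Grouping in that set then needs no further rule.
- **Safety Set.** State that it is summarised by treatment actually received, and fix before unblinding how a subject given both products is classified.

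The change is to SAP wording only. Planned sample size, significance level and trial procedures are unaffected. The one downside is that the FAS estimate is diluted, by the amounts shown above, if a wrong-arm error occurs.
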